It is expected that Visit 1 of trial 1407-0005 will be performed on the same day of the EOT Visit of trial 1407-0030 in both patient groups. In the event that patients completing Part 2 of trial 1407-0030 are not able to be entered immediately into the extension trial due to administrative reasons (e.g., pending protocol approval, availability of trial medication), Visit 1 of the extension trial may be delayed for no more than 16 weeks.

The treatment period in this trial will be approximately 6 years.

Figure 6.1: 1

Trial 1407-0005 dose assignment/reassignment for patients entering from Part 1 of trial 1407-0030

[figure not shown]
[figure not shown]

Figure 6.1: 2

Trial 1407-0005 dose assignment for patients entering from Part 2 and continuing from Part 1 of trial 1407-0030

Dose selection at Week 12 is based on the safety and tolerability data from the SRD Trial 1407.1 and the MRD Trial 1407-0002, and will be contingent on DMC evaluation of all available data from Phase II trial 1407-0030. For patients entering from Part 1 of trial 1407-0030, if an unacceptable risk regarding the safety of the 200 mg dose level is reported by the DMC, the open label BI 730357 dose assignments beginning at Week 12, is to be altered to assign all patients to the 100 mg *q.d.* dose group.

All patients entering from Part 2 of trial 1407-0030 are to receive the 400 mg *q.d.* dose, as long as no unacceptable risks are identified during Part 2 of trial 1407-0030. Once Part 2 patients begin enrolling in this trial, existing patients receiving 100 mg *q.d.* in this trial will be given the option to titrate up to the 200 g *q.d.* dose, if the investigator determines that the Patients may benefit from the higher dose.

The first Part 2 patients enrolled in this study on December 10, 2020 and at that time all Part 1 patients had been in the study more than 12 weeks and had titrated to 100 mg *q.d.*

Subjects will be analyzed according to the treatment to which they were treated. The following study periods based on actual start and stop dates of study treatment administration are defined as follow.

Table 6.1: 1 Definition of Treatment Periods

Analysing Treatment Period	Start Date	Stop Date
Screening [#]	NA	NA
On-treatment*	Date/Time of the first administration of trial treatment	Date of the last administration of trial treatment + REP
Follow-up	Date of the last administration of trial treatment + REP+1 day	Date of the last per protocol visit

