- If AE onset date \leq date of End of Treatment visit in the preceding trial (1407-0030) < AE worsening date < date of first intake after week 12 re-assignment, then the AE is assigned to “first 12 weeks of treatment”.

If an AE worsening occurs on the day of week 12 visit, actual time between AE onset and study medication taken will be compared to determine AE time period (first 12 weeks, second treatment period).

If the subject discontinues before the day of week 12 visit, date of first intake after week 12 re-assignment will be missing, the AE worsening will still be assigned to “first 12 weeks of treatment”.

- If date of first intake after week 12 re-assignment \leq AE worsening date \leq date of last intake + 7 days, then the AE is assigned to “second treatment period”.

For patients who rolled over from Part 1 of the 1407-0030 trial if the onset date of an AE occurs prior to Week 12 and continues beyond Week 12 with a worsening RCTC grade after Week 12 then the AE will be captured as a TEAE both during the first 12-week period of 1407-0005 (as a new-onset TEAE) and during the second treatment period (beyond Week 12, as a worsening-TEAE).

Because there is no scheduled titration for patients who rolled over from Part 2 of trial 1407-0030 adverse events will only be summarized for the entire treatment period and will not be summarized for the first 12 weeks and after 12 weeks for these patients.

Due to differing doses, differing titration schedules and different timeframe for entering this study between patients from part 1 and part 2 of trial 1407_00030, several sets of adverse event analyses, each consisting of 11 summaries, will be presented:

- Events up to 12 weeks for patients who rolled over from Part 1 of trial 1407_00030 with treatment columns BI 25 mg, BI 50 mg, BI 100 mg and BI 200 mg
- Events after 12 weeks for patients who rolled over from Part 1 of trial 1407_00030

with treatment columns BI 25 mg/BI 100 mg, BI 50 mg/BI 100 mg, BI 100 mg/BI 100 mg and BI 200 mg/ BI 200mg.

- All events for patients who rolled over from Part 2 of trial 1407-0030 with treatment column BI 400 mg
- All events from all patients who rolled over from trial 1407-0030 (part 1 and part 2 combined) where events are classified under the treatment at onset in 1407-0005 with treatment columns BI 25 mg, BI 50 mg, BI 100 mg, BI 200 mg and BI 400 mg

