Patients from part 1 of trial 1407_00030 who discontinue study treatment prior to Week 12 will be excluded from the second and fourth sets of analyses above. Due to varying length of exposure to the various doses, exposure adjusted incidence rates will be presented in addition to number and percentage of patients with events in the fifth set above (classification by dose at onset).

For the analysis of other safety data (laboratory data, vital signs ,suicidal ideation) summaries will be presented for the entire study, for the first 12 weeks of the study and after 12 weeks on study. For these outputs data from patients who rolled over from Part 1 and Part 2 of study 1407-0030 will be combined. In some of these data displays each treatment appears on a separate page. If deemed appropriate, additional displays showing descriptive statistics with figures for selected outcomes will be presented.

For efficacy summaries of response at Week 24 all patients from Part 1 of trial 1407-0030 will have data will be grouped as follows:

- 100 mg patients from part 1 of trial 1407-0030
 - 25 mg/100mg
 - 50 mg/100 mg
 - 100 mg/100mg
- 200 mg patients from part 1 of trial 1407-0030
- All patients from part 1 of trial 1407-0030
- 400 mg patients from part 2 of trial 1407-0030
- All patients from part 1 and part 2 of trial 1407-0030 combined

For efficacy summaries of time to loss of response data will be grouped as follows:

- 100 mg patients from part 1 of trial 1407-0030 (combing 25 mg/100mg, 50 mg/100 mg and 100 mg/100mg)
- 200 mg patients from part 1 of trial 1407-0030
- 400 mg patients from part 2 of trial 1407-0030

Efficacy response at Week 12 and 36 for patients from Part 2 of trial 1407-0030 will be summarized.

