6.3 SUBJECT SETS ANALYSED

There are two patient sets defined in this trial:

- Enrolled Set (ES)

[figure not shown]
This patient set includes all patients who signed the informed consent form and were also enrolled, regardless whether the patient was treated with trial medication or not.

[figure not shown]
- Treated Set (TS)

The TS includes all patients in the ES who received at least 1 dose of trial medication and is based on the actual treatment received at enrollment visit

The ES will be used for patient disposition.

The TS will be used for demographics, baseline characteristics, treatment exposure, analyses of all efficacy endpoints and safety analyses (including adverse events, laboratory measurements, vital signs, and ECG).

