7. PLANNED ANALYSIS

The format of the listings and tables will follow the standards defined in the BI corporate guideline “Reporting of clinical trials and project summaries” .

The individual values of all patients will be listed, sorted by treatment, patient number and visit. The listings will be included in Appendix 16.2 of the CTR.

For EoT tables, the set of summary statistics is: N / Mean / SD / Min / Median / Max.

For appendix tables, the set of summary statistics is: N / Mean / SD / Min / Q1 (lower quartile) / Median / Q3 (upper quartile) / Max.

Tabulations of frequencies for categorical data will include all possible categories and will display the number of observations in a category as well as the percentage (%) relative to the respective treatment group. Percentages will be rounded to one decimal place. The category “missing” will be displayed only if there are actually missing values. Percentages will be based on all patients in the respective patient set no matter whether they have non-missing values or not.

No interim analysis is planned for this trial.

For patients from Part 1 of the 1407-0030 trial planned treatment for first 12 weeks of treatment is defined as treatment patient received at the end of 1407-0030. Planned treatment for after 12 weeks (Period 2) is defined as the treatment patient assigned from IVRS at week 12 visit (V2). For patients who titrate according to the protocol from 100 g *q.d.* dose to 200 g *q.d.* dose, if the investigator determines that the patient may benefit from the higher dose, 200 g *q.d.* dose will be the planned dose after the titration.

Subject data listings of data used in the analyses (i.e. demographic and baseline characteristics and key efficacy endpoints) will also be provided and included in Appendix 16.2 of the CTR.

Disposition of the patient population participating in the trial will be summarised by presentation of the frequency of patients screened, entered, screened but not entered, treated, entered but not treated. Within treated patients, data for patients rolled over from Part 1 of trial 1407-00030 will be summarized by treatment periods (period 1 - first 12 weeks of treatment and period 2 – open label treatment after week 12) for treatment ongoing patients, patients complete planned treatment period and patients who are prematurely discontinued, by reason.

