7.4 PRIMARY ENDPOINT(S)

7.4.1 Primary analysis of the primary endpoint(s)

The primary endpoint is the occurrence of treatment emergent adverse events (TEAEs) up to Week 288. The primary analysis will be based on the exposure adjusted rate of patients reporting a treatment emergent adverse event (TEAE) up to Week 288.

Exposure-adjusted adverse event incidence rates will be calculated using the following approach:

- The incidence rate (per 100 subject years) of a selected adverse event (also known as the incidence density rate or person-time incidence rate) is defined as the number of subjects experiencing the adverse event per treatment group during the time at risk divided by the total time of subjects at risk in that treatment group to contribute an event to the analysis multiplied by 100 (per 100 subject years), where for each subject and each TEAE preferred term:

$$\text{Time at risk [subject years]} = (\text{date of first onset of AE} - \text{study drug start date} + 1) / 365.25$$

If, for a subject, no treatment emergent adverse event occurred for the preferred term, then the time at risk will be censored at the minimum of (date of death; drug stop date + 7 days; last contact date).

- For each AE, the incidence rate will therefore be calculated as:

$$\text{Incidence rate [per 100 subject years (pt-yrs)]} = 100 * \text{number of subjects with TEAE} / \text{Total TEAE-specific time at risk [subject years].}$$

Exact 95% confidence intervals (CI) around the observed AE incidence rate will also be provided using exact Poisson regression.

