1	SMQ Drug Related Hepatic Disorders	SMQ Drug related hepatic disorders – comprehensive search (20000006)
2	SMQ Opportunistic infections	MedDRA SMQ Opportunistic Infections (narrow)
3	Tuberculosis related terms	BIcMQ “Tuberculosis related terms” BIcMQ (30000107)(broad)
4	Severe infections	SOC “Infections and infestations” with eCRF severity grade >= Rheumatology Common Toxicity Criteria (RCTC) Grade 3
5	Gastritis related terms	
 BIcMQ Gastritis (broad) [32008061]

This column indicates whether the Term(s) provided in the second column are MedDRA preferred terms (PT), Standardised MedDRA Queries (SMQ) or BI customised MedDRA Queries (BIcMQ).

In addition, adjudicated MACE (provided by [REDACTED] will be summarized by indication, treatment, primary system organ class and preferred term.

The user defined AE categories will be updated accordingly with Safety SAP updates.

The following periods will be defined for assessing adverse events for patients from Part 1 of the 1407-0030 trial.:

- First 12 weeks of treatment
- Second treatment period

For patients from Part 1 of the 1407-0030 trial, AEs with onset date on day of week 12 visit, the AE onset time will be compared with first drug administration time of the dose dispensed at the Week 12 visit to determine AE period. The treatment label for second period will be a combination of actual treatment in first 12 weeks of treatment and second period treatment.

Additionally an analysis including patients from both parts of the 1407-0030 trial will be performed in which adverse events are classified under the dose the patient was receiving at the onset of the TEAE.

AE summaries

An overall summary of adverse events will be presented. The frequency of patients with adverse events will be summarized by treatment, primary system organ class and preferred term according to MedDRA. Separate tables will be provided for patients with:

- Drug-related AEs
- AESIs

- AEs leading to discontinuation
- Serious AEs
- Other significant AEs
- AE by worst RCTC intensity
- Investigator defined drug-related serious AEs
- User defined AE categories

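### SAP 7.4.1 does not divide time at risk at a dose change, although exposure-adjusted TEAE rates are to be shown by dose at onset; this affects Part 1 dose-changers only

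*SAP*

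**What the plan says.** **Numerator.** SAP 6.1 lists an adverse event set, covering both parts, in which "events are classified under the treatment at onset in 1407-0005", with columns for 25, 50, 100, 200 and 400 mg. SAP 7.8.1 repeats the rule: "adverse events are classified under the dose the patient was receiving at the onset of the TEAE". SAP 6.1 then attaches the exposure-adjusted rates to this set: these "rates will be presented in addition to number and percentage of patients with events in the fifth set above (classification by dose at onset". The same sentence gives the reason, namely that exposure to the various doses differs in length.

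**Denominator.** SAP 7.4.1 makes the exposure-adjusted TEAE rate the primary analysis. In words, the denominator is the "total time of subjects at risk in that treatment group to contribute an event to the analysis". The equation below those words starts at the study drug start date and ends at the first onset of the preferred term. For a subject without that event, "the time at risk will be censored at the minimum of (date of death; drug stop date + 7 days; last contact date".

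**Dose changes.** Under Protocol 3.1 and SAP 6.1, Part 1 patients on placebo, 25 mg or 50 mg move to 100 mg at Week 12. Patients on 100 mg may later move to 200 mg.

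**Related text.** SAP 6.1 says "Subjects will be analyzed according to the treatment to which they were treated". For patients who titrate to 200 mg, SAP 7 says that this "dose will be the planned dose after the titration". SAP 7.7 divides days of exposure by actual treatment at a switch. SAP 6.3 says that the Treated Set "is based on the actual treatment received at enrollment visit".

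**The concern.** A rate by dose needs events on that dose over time on that dose. The numerator follows the dose at onset, but the equation gives each subject one undivided clock per preferred term. For a patient who goes from 25 to 100 mg at Week 12, the SAP does not say which column receives the roughly 12 weeks before the change and the possibly five years after it. The Week 12 rules in SAP 6.1 assign events to periods, not person-time. SAP 7.7 defines days on drug, not event-specific time at risk, and 7.4.1 does not refer to it.

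Even a programmer who assumes a split has to invent two rules: whether the 7-day tail applies at a switch, and whether a first onset on an earlier dose ends risk on later doses. Two competent programmers could therefore produce different tables for the primary safety endpoint by dose. The columns most exposed are 25 and 50 mg, where on-dose time in this trial is only about 12 weeks.

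**Working it through.** The documents give no incidence rate or person-time total, so there is no planned figure to reproduce. The check applies the 7.4.1 clock with and without a split.

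**Inputs from the documents.** Dose change at Day 84 (SAP 6.7), so t1 = 84/365.25 = 0.230 years. Last planned treatment visit at Week 288 (Day 2016).

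**Assumptions.** Constant event rate r = 0.10 per year on every dose; no dropout; follow-up to T = Week 96, 144 or 288 (1.840, 2.760 or 5.520 years); one 100/100 mg patient per Week 12 switcher in the pooled 100 mg column; no later titration; the 7-day tail ignored.

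**Quantities per patient.**
- Undivided clock: D = (1 - exp(-rT))/r = 1.681, 2.412, 4.242
- First event before the change: E1 = 1 - exp(-r·t1) = 0.02274
- First event after it: E2 = exp(-r·t1) - exp(-rT) = 0.1453, 0.2184, 0.4014
- Clock contributed by patients with an event before the change: te1 = (1 - exp(-r·t1)(1 + r·t1))/r = 0.002604
- Any event, 100/100 mg patient: F = 1 - exp(-rT) = 0.1681, 0.2412, 0.4242

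**Rates per 100 patient-years (true value 10)**

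| Allocation of time | Column | Formula | Week 96 | Week 144 | Week 288 |
|---|---|---|---|---|---|
| A: all to entry dose | 25/50 mg | 100·E1/D | 1.35 | 0.94 | 0.54 |
| A | 100 mg, pooled 1:1 | 100·(E2+F)/D | 18.6 | 19.1 | 19.5 |
| B: all to dose at onset, or last dose if event-free | 25/50 mg | 100·E1/te1 | 873 | 873 | 873 |
| B | 100 mg, pooled 1:1 | 100·(E2+F)/(2D-te1) | 9.33 | 9.53 | 9.73 |
| Split at dose change | every column | events on dose / time on dose | 10.0 | 10.0 | 10.0 |

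Under A the 100 mg column receives the switchers' later events but none of their time. Under B the 25 and 50 mg columns contain only patients who had an event there, so the rate is close to 100 × 2/t1 = 870 whatever the true rate.

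**The same in counts.** Assume 40 patients go from 25 to 100 mg (the top of the synopsis range for 25 mg): 2 have a first onset on Day 42, 8 on Day 365, and 30 have none up to Day 2016 + 7.
- Undivided time: (2×42 + 8×365 + 30×2023)/365.25 = 174.38 patient-years.
- Split time: 25 mg (2×42 + 38×84)/365.25 = 8.97; 100 mg (8×281 + 30×1939)/365.25 = 165.42. These sum to 174.38 after rounding.
- 25 mg rate: split 2/8.97 = 22.3 per 100 patient-years (exact 95% CI 2.7 to 80.6); under A 2/174.38 = 1.15 (0.14 to 4.14); under B 2/(84/365.25) = 870.
- 100 mg rate: split 8/165.42 = 4.84; under B 8/174.15 = 4.59.

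Titration from 100 to 200 mg raises the same problem, but the documents give neither the number of titrators nor their dates. Any figure for the 200 mg column would rest on assumed dates and mixes, so none is given.

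**The case against.** The best defence is that the split is already implied. The verbal definition in 7.4.1 confines the denominator to time at risk within the treatment group, and a patient can contribute an event to the 25 mg column only while on 25 mg. SAP 6.1 says that the rates exist because time on the various doses differs, and SAP 7.7 splits exposure by actual treatment. On this reading the equation is generic and needs only dose-specific start and stop dates. That is persuasive about intent, and it stands. It does not supply the dates, the handling of the 7-day tail at a switch, or a repeat-event rule.

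A reader might infer from SAP 6.3 that person-time is meant to follow the enrolment dose, as in allocation A. The documents do not support that. The same Treated Set is used for treatment exposure, which 7.7 divides at the switch, and for adverse events classified by dose at onset. The enrolment label therefore does not fix the column.

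It is also fair to say that A and B produce tables that look wrong on sight, at least in the low-dose columns. They mark the ends of a literal reading and are not forecasts of what will be programmed. B's error in the 100 mg column, 3-7%, could pass unnoticed.

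Finally, parts of the SAP are redacted, including an entry after 7.4.1 in the contents list and the reference for the adverse event guideline cited in 7.8.1. A person-time convention may exist there. The point is therefore made only about the visible text.

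**Conclusion.** The point holds as a gap between the formula and the table it serves. A split by dose was intended, but the visible equation does not carry it out. Taken literally for Part 1 dose-changers (25 or 50 mg, or any placebo entrant, to 100 mg at Week 12; optionally 100 to 200 mg later), it mismatches numerator and denominator. The distortion can be very large in the 25 and 50 mg columns, in either direction. In the pooled 100 mg column it ranges from a small understatement to nearly double. These sizes rest on the assumed constant rate, follow-up and 1:1 mix; the SAP states neither allocation.

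A reader might conclude that the primary analysis as a whole is invalid. The documents do not support that. Patients on 400 mg, on 200/200 mg and on untitrated 100/100 mg have one dose throughout and are unaffected. Protocol 7.2 plans no hypothesis test, and the other adverse event sets in SAP 6.1 show results by period and dose or by dose sequence. The harm is limited to the descriptive comparison of TEAE rates by dose. It should be fixed before those tables are programmed.

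**What to change.** In SAP 7.4.1, for the dose-at-onset rates, define time at risk per subject, preferred term and dose segment:
- **Start:** first intake of that dose in 1407-0005.
- **End:** the earliest of first onset of that term on that dose, first intake of the next dose, last intake + 7 days, death, last contact, or Week 288. Ending at the next dose's first intake matches the SAP 6.1 rule that assigns events from that intake to the second period.
- **Placebo:** keep any placebo time out of the active-dose columns.
- **Repeat events:** state one rule and apply it to numerator and denominator alike, for example counting the first onset of the term within each dose segment.

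In SAP 6.1, refer to the dose-at-onset set by name. The text calls it the fifth set, but only four are listed and it is the fourth. Simply renumbering it would collide with the sentence excluding patients who stop before Week 12 from the second and fourth sets, and would remove their low-dose events and time. State that this exclusion does not apply to the dose-at-onset set.

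The cost is a few sentences of SAP text and start/stop person-time programming on dose dates already needed for SAP 7.7. No new data are needed and trial conduct does not change.

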7.5 SECONDARY ENDPOINT(S)

7.5.1 Key secondary endpoint(s)

This section is not applicable as no key secondary endpoint has been specified in the protocol.

7.5.2 (Other) Secondary endpoint(s)

For the convenience of writing and reviewing, all PASI and sPGA endpoints at different time points (secondary and further clinical endpoints) are first described generally in this section prior to addressing each secondary objective specifically.

Psoriasis Area and Severity Index (PASI)

Details for scoring Psoriasis Area and Severity Index (PASI) and its components are described in Section 10.1 of the CTP. The percent reduction from baseline is calculated by % PASI reduction from baseline = $((\text{PASI at baseline} - \text{PASI at Visit X}) / \text{PASI at baseline}) * 100$, at all visits with PASI collected. Achieving an X% or larger reduction from baseline PASI score is denoted as PASI X.

Static Physician's Global Assessment (sPGA)

The sPGA is scored using the following levels of assessment:

0 - clear 1 - almost clear 2 - mild 3 - moderate 4 - severe

Secondary Outcome Achievement of PASI50/PASI75/PASI90/PASI100 at Week 24

Descriptive statistics of the percentage of patients who achieve a PASI score of at least 50% (PASI 50), 75% (PASI 75), 90% (PASI90) and 100% (PASI100) reductions from baseline at Week 24 will be tabulated for each treatment group. The number of patients, number of patients attaining the PASI response, percentage of patients attaining the PASI response at Week 24 with corresponding exact 95% confidence interval will be presented based on the Clopper Pearson method.

The primary analysis of these secondary outcomes will be based on an observed case analysis.

Secondary Outcome Achievement of sPGA clear or almost clear at Week 24

Descriptive statistics of the percentage of patients who achieve sPGA of clear or almost clear (sPGA score of 0 or 1 ("clear or almost clear")) at Week 24 will be tabulated for each treatment group. The number of patients, number of patients attaining the sPGA response, percentage of patients attaining the sPGA response at Week 24 with corresponding exact 95% confidence interval will be presented based on the Clopper Pearson method.

The primary analysis of these secondary outcomes will be based on an observed case analysis.

Secondary Outcome Achievement of sPGA clear at Week 24

Descriptive statistics of the percentage of patients who achieve sPGA of clear (sPGA score of 0 ("clear ")) at Week 24 will be tabulated for each treatment group. The number of patients, number of patients attaining the sPGA response, percentage of patients attaining the sPGA response at Week 24 with corresponding exact 95% confidence interval will be presented based on the Clopper Pearson method.

The primary analysis of these secondary outcomes will be based on an observed case analysis.

Secondary Outcome Time to Loss of PASI50/PASI75/PASI90/PASI100 for patients who achieve the response up to Week 288

For the time to loss of response (PASI 50/ PASI 75/ PASI 90/ PASI 100) the time to event will be calculated as

- Time to first loss (with observed event) = [date of first loss] – [date of first visit with qualifying response] + 1
- Time to first loss (censored) = [date of last visit with qualifying response] – [date of first visit with qualifying response] + 1
- If a patient never attains PASI 50/ PASI 75/PASI 90/PASI 100 then the patient will not contribute to the analysis of this outcome.

Time to loss of response will be analysed descriptively by Kaplan Meier curves. If at least 50% of patients lose response, the median time to loss of response will be estimated median of time to loss with 95% confidence interval will be presented.

Secondary Outcome Time to Loss of sPGA clear or almost clear at Week 24 for patients who achieve the response up to Week 288

For the time to loss of response (sPGA clear or almost clear), the time to event will be calculated as:

- Time to first loss (with observed event) = [date of first loss] – [date of first visit with qualifying response] + 1
- Time to first loss (censored) = [date of last visit with qualifying response] – [date of first visit with qualifying response] + 1
- If a patient never attains sPGA clear or almost clear then the patient will not contribute to the analysis of this outcome.

[figure not shown]
Time to loss of response will be analysed descriptively by Kaplan Meier curves. If at least 50% of patients lose response, the median time to loss of response will be estimated median of time to loss with 95% confidence interval will be presented.

Secondary Outcome Time to Loss of sPGA clear at Week 24 for patients who achieve the response up to Week 288

For the time to loss of response (sPGA clear), the time to event will be calculated as:

- Time to first loss (with observed event) = [date of first loss] – [date of first visit with qualifying response] + 1
- Time to first loss (censored) = [date of last visit with qualifying response] – [date of first visit with qualifying response] + 1
- If a patient never attains sPGA clear then the patient will not contribute to the analysis of this outcome.

Time to loss of response will be analysed descriptively by Kaplan Meier curves. If at least 50% of patients lose response the median time to loss of response will be estimated median of time to loss with 95% confidence interval will be presented.

